9. SUBJECT ACCOUNTABILITY

9.1. *Point of Enrollment*

Subjects will be considered enrolled into the NAVIGATE X4 Clinical Study at the time of informed consent form execution. All subject enrollments will be counted against the enrollment ceiling for the study.

9.2. *Withdrawal*

All subjects enrolled in the clinical study (including those withdrawn from the clinical study or lost to follow-up) shall be accounted for and documented. If a subject withdraws from the clinical investigation, the reason(s) shall be reported. If such withdrawal is due to problems

December 17, 2013
FINAL

Boston Scientific
NAVIGATE X4 Study Protocol
90874504 Version AB
Page 30 of 101

related to investigational device safety or performance, the investigator shall ask for the subject's permission to follow his/her status/condition outside of the clinical study.

Reasons for withdrawal may include physician discretion, subject choice to retire consent, loss to follow-up, or death. While study withdrawal is discouraged, subjects may withdraw from the study at any time, with or without reason, and without prejudice to further treatment. All applicable electronic case report form (eCRFs) up to the point of subject withdrawal and an "End of Study" eCRF must be completed. For subjects who are "lost-to-follow-up" the investigator/center should have at least three documented attempts to contact the subject prior to completion of the "End of Study" eCRF. Additional data may no longer be collected after the point at which a subject has been withdrawn from the study or withdraws his/her consent, for whatever reason. All open adverse events should be closed or documented as chronic. Data collected up to the point of subject withdrawal may be used.

9.3. *Subject Status and Classification*

All patients who sign the Informed Consent form are considered enrolled in the study and count towards the enrollment ceiling. Subjects will be classified in the study database as follows:

Intent - refers to a subject who has been enrolled, but then does not undergo an implant procedure. The original Informed Consent form and screening documentation for intent patients should be maintained in the Center's files. There are no follow-up requirements for intent subjects; intent subjects must be withdrawn from the study.

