Partial Attempt – refers to a subject who has been enrolled and has had anesthesia administered in preparation for the surgical implant procedure, but does not have an ACUITY X4 or RELIANCE 4-FRONT lead introduced into their vasculature. There are no follow-up requirements for partial attempt subjects; partial attempt subjects must be withdrawn from the study.

Note: In this case since neither study lead was implanted, US subjects may not be implanted with an AUTOGEN X4 CRT-D (while it is investigational)

Attempt - refers to a subject who 1) has been enrolled in the NAVIGATE X4 Study, 2) has had anesthesia administered in preparation for the surgical implant procedure, 3) has had either the ACUITY X4 or RELIANCE 4-FRONT lead introduced into the subject's vasculature, but 4) is not successfully implanted with either the ACUITY X4 lead or RELIANCE 4-FRONT lead.

Note: In this case since neither the RELIANCE 4-FRONT lead nor the ACUITY X4 lead was implanted, US subjects may not be implanted with an AUTOGEN X4 CRT-D (while it is investigational)

Attempt subjects must be followed 30 ± 7 days post-attempted ACUITY X4 and/or RELIANCE 4-FRONT lead implant to assure there are no associated adverse events, or to assure the resolution of any adverse events associated with the attempted ACUITY X4 and/or RELIANCE 4-FRONT lead implants. These subjects must be withdrawn from the study after satisfying the 30 ± 7 day follow up.

Implant - refers to a subject who is successfully implanted and/or tested with the ACUITY X4 and/or RELIANCE 4-FRONT Lead(s) per the study protocol. These subjects are

December 17, 2013
FINAL

Boston Scientific
NAVIGATE X4 Study Protocol
90874504 Version AB
Page 31 of 101

followed in accordance with the follow-up schedule included in this protocol and included in all analyses of safety, effectiveness, and performance.

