11.1.3. Statistical Methods

To assess safety of the ACUITY X4 leads, the Kaplan-Meier six month (180-day) complication-free rate will be calculated. [redacted]
The analysis will be conducted when the last 6-month follow-up is completed [redacted]
[redacted] Data from all implanted or attempted [redacted] [redacted] leads will be included in the endpoint analysis.

December 17, 2013
FINAL

Boston Scientific
NAVIGATE X4 Study Protocol
90874504 Version AB
Page 49 of 101

[REDACTED]

The exact follow-up time for each ACUITY X4 lead in the 180-day post-implant period will be included in the analysis via Kaplan-Meier methodology. The leads that fail to reach 180 days of follow-up (without experiencing an endpoint event prior to their end of follow-up in the period) will be censored at the time of their end of follow-up in the period. Because non-informative censoring cannot be assumed for these leads, a tipping point analysis will be performed to determine the potential effects these censored leads could have on the results if full information on each lead was present. The tipping point analysis will assign each lead that was censored prior to 180 days as either having or not having an endpoint event. The tipping point will be determined by the point at which the endpoint results turn from passing (null hypothesis) to failing (null hypothesis rejected). An exact binomial test will be performed for the tipping point analysis.

11.1.4. ACUITY X4 Primary Effectiveness Endpoint 1

The first effectiveness endpoint for ACUITY X4 is pacing capture thresholds (PCT) in the programmed configuration. This endpoint will be evaluated at 3 months post-implant. [REDACTED] For this endpoint, responders will be defined as subjects with $PCT \leq 2.5$ V in the programmed configuration.

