11.2.1.3. Statistical Methods

Data from all subjects implanted or attempted with a RELIANCE 4-FRONT lead will be eligible for inclusion in the endpoint analysis. All RELIANCE 4-FRONT leads [REDACTED] will be pooled for this analysis.

The lead-related complication-free rate from date of implant (or date of attempt, for leads attempted but not implanted) through 91 days post-implant will be calculated using Kaplan-Meier methodology. The 95% one-sided lower pointwise confidence limit of the complication-free rate will be calculated via log-log methodology for all eligible subjects contributing to the analyses and compared to the performance goal of 93%. If the lower confidence limit exceeds 93%, the null hypothesis will be rejected.

Each lead's exact follow-up time in the 91 days post-implant will be included in the analysis via Kaplan-Meier methodology. The leads that fail to reach 91 days of follow-up (without

December 17, 2013
FINAL

Boston Scientific
NAVIGATE X4 Study Protocol
90874504 Version AB
Page 55 of 101

experiencing an endpoint event prior to their end of follow-up in the period) will be censored at the time of their end of follow-up in the period. Because non-informative censoring cannot be assumed for these leads, a tipping point analysis will be performed to determine the potential effects these censored leads could have on the results if full information on each lead was present. The tipping point analysis will assign each lead that was censored prior to 91 days as either having or not having an endpoint event. The tipping point will be determined by the point at which the endpoint results turn from passing (null hypothesis) to failing (null hypothesis rejected). An exact binomial test will be performed for the tipping point analysis.

11.2.2. RELIANCE 4-FRONT Primary Safety Endpoint 2

To satisfy the safety assessment requirements of the US Food and Drug Administration (FDA), safety of the RELIANCE 4-FRONT Leads will also be evaluated by the lead-related CFR from three months post-implant through 24 months post implant based on complications that are related to the RELIANCE 4-FRONT Lead during that period. The same definition of lead-related complication will be used for both RELIANCE 4-FRONT Primary Safety Endpoint 1 and Primary Safety Endpoint 2.

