
Device Deficiency
 
Ref: ISO 14155-2011
 
Ref: MEDDEV 2.7/3 12/2010
	
A device deficiency is any inadequacy of a medical device with respect to its identity, quality, durability, reliability, safety or performance.
 
NOTE 1: Device deficiencies include malfunctions, misuse or use errors, and inadequate labeling.

Abbreviations: **EC**=Ethics Committee; **IRB**=Institutional Review Board

December 17, 2013
FINAL

Boston Scientific
NAVIGATE X4 Study Protocol
90874504 Version AB
Page 79 of 101

Underlying diseases are not reported as AEs unless there is an increase in severity or frequency during the course of the NAVIGATE X4 Clinical Study. Death should not be recorded as an AE, but should only be reflected as an outcome of a specific SAE (see Table 17 for AE definitions).

Any AE experienced by the study subject after informed consent, whether during or subsequent to the procedure, must be recorded in the eCRF.

Refer to Section 18 for the known risks associated with the study device(s).

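### Subjects left with neither study lead are withdrawn at day 23–37, although their attempted leads belong to 180-day and 91-day primary safety endpoints, so the plan creates avoidable censored leads

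*Protocol*

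**What the plan says.** Protocol section 9.3 defines an Attempt subject as one in whom a study lead was introduced into the vasculature without either study lead being successfully implanted. The accompanying note confirms the scope: "In this case since neither the RELIANCE 4-FRONT lead nor the ACUITY X4 lead was implanted". These subjects have one follow-up at 30 ± 7 days, meant to rule out or see through adverse events of the attempt, and then: "These subjects must be withdrawn from the study after satisfying the 30 ± 7 day follow up". Section 9.2 adds: "Additional data may no longer be collected after the point at which a subject has been withdrawn from the study".

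The primary safety endpoints nevertheless include these leads.

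- **ACUITY X4.** Section 11.1.1 counts complications of attempted implants, and section 11.3.2 defines the analysis set as subjects implanted or attempted. Section 11.1.3 uses a 180-day Kaplan-Meier rate. It opens its censoring rule with "The leads that fail to reach 180 days of follow-up", says that non-informative censoring cannot be assumed for those leads, and plans a tipping-point analysis with an exact binomial test.
- **RELIANCE 4-FRONT Primary Safety Endpoint 1.** Section 11.2.1.3 says: "Data from all subjects implanted or attempted with a RELIANCE 4-FRONT lead will be eligible for inclusion in the endpoint analysis". The horizon is 91 days, the goal is 93%, and the censoring and tipping-point rules are the same.

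Two further passages bear on the point. Section 8.2 makes RELIANCE optional in Study Phase 1. Section 10.5.4 says that when another of the sponsor's LV leads replaces a failed ACUITY X4, data on it follow sections that include the three-month and semi-annual measurements. It makes no exception for Attempt subjects.

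**The concern.** An Attempt lead without an event by its single visit cannot reach the endpoint horizon. The protocol itself makes it an unknown in an analysis that already concedes that its censoring may be informative. Kaplan-Meier then gives these leads the later hazard of successfully implanted leads, with no data to support that. A new lead-related complication after withdrawal is not captured. Nor is an open adverse event that becomes a complication only later, for example through an invasive intervention as described in section 19.3.1 and Table 20.

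How long a failed ACUITY attempt is observed also depends on another lead. With a RELIANCE lead in place the subject is an Implant and stays on the full schedule. In Phase 1, with a commercial RV lead, the same failed attempt makes the subject an Attempt, seen for about 30 days.

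At stake are the completeness of the primary safety data and the strength of the planned robustness check.

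**Working it through.** **1. Unobserved time.** The visit falls between day 30 − 7 = 23 and day 30 + 7 = 37.

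- 180-day endpoint: 180 − 37 = 143 to 180 − 23 = 157 days unobserved; 143/180 = 79%, 157/180 = 87%.
- 91-day endpoint: 91 − 37 = 54 to 91 − 23 = 68 days unobserved; 54/91 = 59%, 68/91 = 75%.

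**2. What is known and what is assumed.** From the documents: cohorts of 534 spiral and 214 straight ACUITY leads (SAP 2.1; 534 + 214 = 748, as stated there), 1876 RELIANCE leads (SAP 2.2), ACUITY goals of 87% and 85% (section 11.1.1.1), and a RELIANCE goal of 93% with a one-sided 95% limit (section 11.2.1.3). Redacted: the ACUITY alpha and which goal applies to which cohort. Not found in the readable text: attempt shares and event rates. The assumptions below are an attempt share f of 1–10%; 10% of attempted leads with an event by day 30; a late risk of 0–5% of attempted leads; and event rates in implanted leads of 8% at 180 days (ACUITY) or 3% at 91 days (RELIANCE), 70% of them by day 30.

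**3. Effect on the Kaplan-Meier rate.** The estimate is S(30) × (1 − late events / leads at risk after day 30). For ACUITY with N = 534 and f = 10%, there are 53.4 attempted and 480.6 implanted leads.

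- Events by day 30: 480.6 × 0.056 + 53.4 × 0.10 = 32.25, so S(30) = 1 − 32.25/534 = 0.9396.
- Late events in implanted leads: 480.6 × 0.024 = 11.53.
- Attempts withdrawn: 0.9396 × (1 − 11.53/453.7) = 0.9157.
- Attempts followed, late risk 5% (2.67 events): 0.9396 × (1 − 14.20/501.7) = 0.9130. Withdrawal makes the rate 0.27 points too high.
- Attempts followed, late risk 0: 0.9396 × (1 − 11.53/501.7) = 0.9180. Withdrawal makes the rate 0.23 points too low, which is conservative.

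The sign changes where event-free attempted leads have the same late hazard as implanted ones: 0.024/0.944 = 2.5%, or 0.9 × 2.5% = 2.3% of all attempted leads. For RELIANCE (N = 1876), the same calculation runs from 0.08 points too low to 0.42 too high at f = 10%. Late events lost are 0 to 2.7 (ACUITY) and 0 to 9.4 (RELIANCE).

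**4. Effect on the tipping-point analysis.** The limit is the largest k with P(X ≤ k) ≤ alpha, where X is binomial with N leads and event probability 1 − goal. Because the pairing of goal and cohort is redacted, all four are shown; expected events are 8% of N.

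| N | Goal | Most events that pass (alpha 2.5% / 5%) | Expected events | Margin |
|---|---|---|---|---|
| 534 | 87% | 54 / 56 | 43 | 11 / 13 |
| 534 | 85% | 63 / 66 | 43 | 20 / 23 |
| 214 | 85% | 21 / 23 | 17 | 4 / 6 |
| 214 | 87% | 18 / 19 | 17 | 1 / 2 |

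For 534 against 87%, 12 or 14 further events turn the result. The event-free Attempt leads available are:

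- f = 1%: 5.3 × 0.9 = about 5. They cannot turn it.
- f = 3%: 16.0 × 0.9 = about 14. This takes 12 of 14 (86%) or all 14 being assigned an event.
- f = 5%: 26.7 × 0.9 = about 24. This takes 12 of 24 (50%) or 14 of 24 (58%).

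These counts treat all other censored leads as event-free; any that are not use up the margin sooner.

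For RELIANCE (1876 against 93%, alpha 5%) at most 112 events pass. At f = 3%, known events are 1819.7 × 0.03 + 5.6 = 60, leaving a margin of 52 against about 51 event-free Attempt leads, so they cannot turn it alone. At 5% there are about 84 against a margin of 49. Such shares are less plausible here. Section 10.5.4 requires an ACUITY implant or attempt in every subject, so a failed RELIANCE lead makes an Attempt only when no ACUITY lead is implanted either. SAP 2.2 also draws part of the 1876 from other studies.

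**The case against.** The strongest reply is that the plan already allows for this. It admits that the censoring may be informative and specifies a tipping-point analysis. Complications up to withdrawal are counted. Section 9.2 has open events closed or documented as chronic and, where withdrawal is due to device safety or performance, has the investigator ask to follow the subject outside the study. Many of the listed lead-related events, such as dislodgment, fracture or abnormal impedance, presuppose a lead in place, so late events after a failed attempt may be rare and the censoring conservative. A worst-case assignment is also not a realistic scenario, and tipping would not overturn the primary Kaplan-Meier result.

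Most of this stands, and it limits the size of the point. It does not remove it. The tipping-point analysis absorbs these leads as unknowns but cannot recover what was not collected. Follow-up outside the study covers only some withdrawals and is not routed into the endpoint.

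Three stronger readings are tempting, and the documents do not support them.

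- **Every failed study-lead implant leads to early withdrawal.** It does not: one study lead in place makes the subject an Implant with full follow-up. Only the final lead of the initial procedure contributes (section 11.3.2, SAP 2.3), so a failed attempt followed by successful implantation of the same lead type is unaffected.
- **Partial Attempts are lost from these endpoints.** Such a subject "does not have an ACUITY X4 or RELIANCE 4-FRONT lead introduced into their vasculature", so there is no attempted lead to analyse.
- **Unresolved complications are lost.** A complication counts when it occurs and ends that lead's time at risk; later resolution does not matter to the endpoint.

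**Conclusion.** The point holds for Attempt subjects only. The mandatory withdrawal cuts their observation to 13–21% of the 180-day window or 25–41% of the 91-day window, in endpoints that include their leads by definition. A reader might infer a material bias in the primary safety result, but the figures do not show one: the shift is about 0.2–0.4 points or less under the assumed ranges, and its sign depends on an unknown late risk. The real cost is avoidable unknowns in the tipping-point analysis. They could decide its outcome in a worst case at an attempt share of about 3% for 534 leads against 87%, and not at 1%. These sizes rest on assumed attempt shares and event rates and on a redacted alpha and goal allocation, so they illustrate and do not predict.

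Section 9.3 also sits uneasily with itself. The visit is meant to assure resolution of adverse events, yet the withdrawal sentence sets a fixed window and is silent on events still open. This is a worthwhile, inexpensive improvement and not a flaw that invalidates the endpoints.

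**What to change.** Make three changes, all confined to data collection and reporting.

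1. In section 9.3, replace mandatory withdrawal of Attempt subjects with continued enrolment for ascertainment of lead-related complications and vital status, to day 91 for an attempted RELIANCE lead and/or day 180 for an attempted ACUITY lead, by one telephone or record-review contact.
2. In sections 11.1.3 and 11.2.1.3, report Attempt leads as a separate group in the tipping-point analysis, so that a reader can see how many unknowns come from failed implants and how many from other loss to follow-up.
3. Reconcile sections 9.2, 9.3 and 10.5.4 on what is collected after a failed ACUITY attempt, and on adverse events still open at the 30 ± 7 day visit.

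Partial Attempts need only a wording check for adverse event recording: section 9.3 says "There are no follow-up requirements for partial attempt subjects; partial attempt subjects must be withdrawn from the study", while section 19.1 says "Any AE experienced by the study subject after informed consent, whether during or subsequent to the procedure, must be recorded in the eCRF". The two should be reconciled.

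The cost is revised protocol and consent wording and minor site work, one remote contact for what is probably a few percent of subjects, with no added procedure or clinic visit. The downside for the sponsor is possibly a few more counted events.

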9.4. Enrollment Controls

To support regulatory requirements approximately 1840 subjects [REDACTED] [REDACTED] will be enrolled per this protocol. Investigational sites will be notified when the enrollment goal for each cohort is close to being reached and once enrollment for each cohort is complete. See Section 7.2 for more information on the study cohorts.

9.5. End-of-Study Action Plan

Boston Scientific Corporation reserves the right to terminate the study, or discontinue implanting one of the two study leads at any stage but intends to exercise this right only for valid scientific or administrative reasons and reasons related to protection of subjects. In the event of this occurrence, BSC will communicate to the investigators of the NAVIGATE X4 Clinical Study. The investigators will be responsible for communicating any information necessary to the subjects. BSC will support the physicians by providing recommendations for ensuring the safety of the subjects and the handling of the investigational devices (AUTOGEN X4 CRT-D, ACUITY X4 leads, and/or RELIANCE 4-FRONT leads) which may include, but are not limited to:

- Standard of care procedures
- More frequent follow ups of the subject and the lead(s) than per standard procedures
- Longer term follow up (beyond consented 5-year period)
- Explantation of ACUITY X4 and/ or RELIANCE 4-FRONT leads
- Explantation of AUTOGEN X4 CRT-D
- Other possible actions

10. STUDY METHODS

10.1. Data Collection

The data collection schedule for this study is shown in Table 7 below. A reminder that the NAVIGATE X4 Clinical Study is [REDACTED] ACUITY X4 is required to be implanted or attempted [REDACTED] and RELIANCE 4-FRONT is [REDACTED] required to be implanted or attempted [REDACTED]

December 17, 2013
FINAL

Boston Scientific
NAVIGATE X4 Study Protocol
90874504 Version AB
Page 32 of 101

Table 7: Data Collection Schedule for NAVIGATE X4 Clinical Study

Procedure/ Assessment	Enroll- ment	Implant	Pre- Discharge	3 Months	6 Months	Semi-annual Visits through 5 Years	Add'l Visits
Timeframe	≤ 30 d prior to Implant	Implant	3-72 h* Clinic Visit	91±21 d [†] Clinic Visit	182±21 d* Clinic Visit	12 Mo: 365±45 d* 18 Mo: 547±45 d* 24 Mo: 730±45 d* 2 ½ Yr: 913±45 d* 3 Yr: 1095±45 d* 3 ½ Yr: 1278±45 d* 4 Yr: 1461±45 d* 4 ½ Yr: 1643±45 d* 5 Yr: 1826±45 d* Clinic Visit	Not specified
ICF Process	X	--	--	--	--	--	--
Subject demographics	X	--	--	--	--	--	--
Physical assessment	X	--	--	--	--	--	--
Medical history	X	--	--	--	--	--	--
PSA measurements for all leads (pacing threshold(s) @ 0.5ms)	--	X (X4 leads, else O	--	--	--	--	--
PA and lateral CXR and/or fluoro image of X4 and 4-FRONT lead distal tip fixation	--	X (Either/ or, not both)		--	--	--	--
Ventricular tachyarrhythmia induction	--	O		--	--	--	--
Shock Therapy for Spontaneous Ventricular Arrhythmias	--	X	X	X	X	X	O
Class I/ III Antiarrhythmic Medications including updates and changes	X	X	X**	X**	X**	X**	O**
Documentation of PaceSafe Programming	--	X	X	X	X	X	O
PG lead measurements (sensed amplitude, impedance, shock lead impedance and PCT) for all implanted leads (pacing threshold(s) for RV and [contact] through 3 Month follow up)	--	X	X	X	X	X	X (if lead- related AE), else O
ECG from PRM documenting LOC	--	X	X	X	--	--	O
Adverse Events	X	X	X	X	X	X	X
Protocol Deviations	X	X	X	X	X	X	X

Legend: X = Required; -- = Not required/ Not applicable; O = Optional;

*Clock Starts after end of implant procedure, day of implant is day 0 and hour 0 is pocket closure

**Collection of Class I/III antiarrhythmic medications for lead-related adverse events

h = hours; d = days; yr = year; AE = Adverse Event; ECG = Electrocardiogram; LOC = Loss of Capture; PG = Pulse Generator; PSA = Pacing System Analyzer

10.2. Study Candidate Screening

Boston Scientific will collect information to document potential subjects who are considered as NAVIGATE X4 Study candidates but are determined not to meet inclusion criteria prior to signing informed consent.

